3.1 Study Design

This is a multicenter, active-treatment extension trial designed to assess the long-term safety and tolerability of oral brexpiprazole (2 and 3 mg/day) as treatment in adults with AAD. Enrollment into the trial will consist of eligible subjects who completed the 12-week treatment in the double-blind, phase 3 efficacy Trial 331-14-213.

The trial will be organized as follows:

Screening/baseline: Subjects who completed Week 12 of the double-blind trial and had no substantial protocol deviations will be screened for eligibility at the last visit of the double-blind trial (ie, Week 12 or ET, if the trial is terminated, visit of Trial 331-14-213). Subjects will sign a separate informed consent form (ICF) for participation in Trial 331-201-00182 before any procedures specific to the extension trial are performed. The assessments from the last visit of the double-blind trial will serve as the baseline measures for Trial 331-201-00182 for any assessment that is not unique to the extension trial. Medical history will be updated, if necessary.

Active Extension Treatment: Eligible subjects from Trial 331-14-213 will receive 12 weeks of daily treatment with brexpiprazole (target doses of 2 or 3 mg/day) in Trial 331-201-00182. Visits will occur at the end of Weeks 1, 2, 6, and 12.

Follow-up: All subjects, whether they complete the trial or are withdrawn prematurely for any reason, will be followed up for a safety evaluation 30 (+ 2) days after the last dose of IMP

Confidential - Proprietary Information

5

22 April 2022

SAP 331-201-00182

during a clinic visit at either the investigator's site or residential facility, as applicable. If a clinic visit is not possible, the subject should be assessed by telephone contact with the subject and a caregiver. For all subjects who terminate early from the trial, all attempts will be made to collect mortality data by telephone contact with the subject's caregiver at Week 16 (relative to baseline visit).

See [Figure 3.1-1](#) for a schematic of the trial design.

SAP 331-201-00182

Screening/Baseline ^b	Treatment Period	Safety Follow-up

Eligible subjects who completed 12 weeks of post-randomization treatment in Trial 331-14-213
	
All subjects will receive brexpiprazole. Subjects randomized to the 2 and 3 mg/day doses of brexpiprazole in Trial 331-14-213 will begin treatment on these doses in Trial 331-201-00182. All subjects who received placebo in Trial 331-14-213 will receive active drug in Trial 331-201-00182.^a
	

Week 12 visit of Trial 331-14-213
	
Duration: 12 weeks
	
Clinic visit or telephone contact Telephone contact at Week 16 for mortality assessment for subjects who terminate early from the trial. Day 30 (+2)/Week 16

Visits at Weeks 1, 2, 6, and 12 Week 12

^aStarting at week 4, 1 dose decrease can occur at any time (scheduled or unscheduled visits) until the end of the trial. In addition, one dose increase can occur but only at the Week 6 scheduled visit. Subjects who received placebo in Trial 331-14-213 will receive active drug in Trial 331-201-00182. Subjects randomized to brexpiprazole and who completed the titration schedule in Trial 331-14-213 (ie, completed Week 4 visit in 331-14-213) will begin treatment on the same dose in this trial. Subjects randomized to brexpiprazole and who have not completed the titration schedule will restart drug in Trial 331-201-00182 dependent on the point in the titration scheme for Trial 331-14-213 that early termination occurred.

SAP 331-201-00182

^bFor subjects who may be offered entry into this trial as a result of early termination of Trial 331-14-213 due to overwhelming efficacy from the interim analysis, the Screening/Baseline will occur at the last visit of the double-blind trial (ie, ET visit of Trial 331-14-213).

Figure 3.1-1 Trial Design Schematic

SAP 331-201-00182

3.2 Trial Treatments

All subjects will receive target doses of 2 or 3 mg/day brexpiprazole in Trial 331-201-00182; these doses were those studied in Trial 331-14-213.

To preserve the blind in Trial 331-14-213, all doses in Trial 331-201-00182 will remain blinded. The first dose taken in Trial 331-201-00182 should be taken one day after the Week 12.

Subjects randomized to the 2 mg/day and 3 mg/day doses of brexpiprazole in Trial 331-14-213 will begin treatment on these same doses in the active-treatment extension Trial 331-201-00182. All subjects who received placebo in Trial 331-14-213 will receive active drug (ie, brexpiprazole) in Trial 331-201-00182.

All subjects will receive target doses of 2 or 3 mg/day brexpiprazole during the trial. Dose adjustments are allowed during the trial. Starting at week 4, one dose decrease can occur at any time (scheduled or unscheduled visits) until the end of the trial. In addition, one dose increase is permitted but only at the Week 6 scheduled visit. Subjects who require an additional dose increase or decrease will be discontinued from the trial. Timing of dose adjustments as outlined above is summarized in the table below.

Dosing Adjustments		
Visit	Decrease ^a	Increase
Week 6	Permitted	Permitted
Unscheduled (week 4 or anytime thereafter)	Permitted	Not Permitted

^aStarting at week 4, 1 dose decrease can occur at any time (scheduled or unscheduled visits) until the end of the trial.

All doses of brexpiprazole will be taken orally once daily, preferably in the morning, and will be administered without regard to meals, and should be taken at approximately the same time each day.

4 Sample Size and Power Justification

The sample size is not based on statistical power considerations. The trial population will be derived from eligible subjects who rollover from the double-blind phase 3 Trial 331-14-213.

5 Data Sets for Analysis and Missing Data

5.1 Data Sets for Analysis

To adequately describe the statistical analyses and reporting, three analysis populations are defined as follows.

SAP 331-201-00182

- Enrolled Sample: comprises all subjects who sign an ICF for the trial and are enrolled into the trial.
- Safety Sample: comprised of those subjects who sign an ICF for the trial and receive at least one dose of brexpiprazole in Trial 331-201-00182.
- Efficacy Sample: comprises all subjects in the Safety Sample who have a baseline assessment and at least one post-baseline assessment for CMAI (Cohen-Mansfield Agitation Inventory) total score.

5.2 Handling of Missing Data

In order to assess the sensitivity of results due to missing data, 2 types of analyses will be performed: last observation carried forward (LOCF) and observed cases (OC). The OC dataset will consist of the actual observations recorded at each visit. The LOCF dataset will include data recorded at a scheduled visit, ie, all OC data, or, if no observation is recorded at that visit, data will be carried forward from the previously scheduled visit. Baseline data will not be carried forward to impute missing values for the LOCF dataset. The OC dataset will be used for analyses at each trial visit and the LOCF dataset will be used for analyses at the last visit.

6 Study Conduct

6.1 Subject Disposition, Completion Rate and Reasons for Discontinuation

Subject disposition will be summarized for the Enrolled Sample by parent study treatment group and overall.

Subject completion rate and reasons for discontinuation will be summarized for the Enrolled Sample by parent study treatment group and overall.

The above summaries will be repeated in subject subgroups as defined by gender (Female and Male), age group (< 65; \geq 65 and < 75; or \geq 75), race (white or other), geographical region (North America or other), and dementia severity (severe, moderate, and mild), where dementia severity will be defined based on Mini Mental State Examination (MMSE) score at baseline as follows:

- Severe: MMSE score \leq 12
- Moderate: MMSE score > 12 and \leq 18
- Mild: MMSE score > 18

SAP 331-201-00182

6.2 Treatment Compliance

Compliance in taking investigational medicinal product is calculated by dividing the number of tablets taken by the total number of tablets the subjects were scheduled to take during the trial period. For lost-to-follow-up subjects, last IMP end date record will be used as the treatment end date.

Number (%) of subjects meeting compliance cut-offs (< 70%, \geq 70% and < 80%, \geq 80% and < 90%, \geq 90%) will be summarized by treatment group.

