Investigational Medicinal Product, Dose, Dosage regimen, Treatment period, Formulation, Mode of Administration:	
The IMP will be supplied as brexpiprazole tablets. Each dose will be supplied in blister cards containing sufficient tablets for 7 (+2) days. When accessed by the site, the eSource method will assign specific blister card number(s) to be dispensed to a subject.
 
All subjects will receive brexpiprazole at target doses of either 2 or 3 mg/day.
 
To preserve the blind in Trial 331-14-213, all doses in Trial 331-201-00182 will remain blinded. Subjects randomized to the 2 mg/day and 3 mg/day doses of brexpiprazole in Trial 331-14-213 will begin treatment on these same doses in the active-treatment extension Trial 331-201-00182. All subjects who received placebo in Trial 331-14-213 will receive active drug in Trial 331-201-00182.
 
For subjects who may be offered entry into this trial as a result of early termination of Trial 331-14-213 due to overwhelming efficacy from the interim analysis, treatment in Trial 331-201-00182 will begin based on randomization and last visit completed in Trial 331-14-213. Subjects who received placebo in Trial 331-14-213 will receive active drug in Trial 331-201-00182. Subjects randomized to brexpiprazole and who completed the titration schedule in Trial 331-14-213 (ie, completed Week 4 visit in 331-14-213) will begin treatment on the same dose in this trial. Subjects randomized to brexpiprazole and who have not completed the titration schedule will restart drug in Trial 331-201-00182 dependent on the point in the titration scheme for Trial 331-14-213 that early termination occurred.
 
All doses of brexpiprazole will be taken orally once daily, preferably in the morning, and will be administered without regard to meals. Brexpiprazole should be taken at approximately the same time each day.

Trial Assessments:	Safety: Adverse event (AE) reporting, clinical laboratory tests, electrocardiograms (ECGs), vital signs, physical and neurological examinations, body weight, body mass index, Mini-Mental State Examination (MMSE), Simpson Angus Scale (SAS) total score, Abnormal Involuntary Movement Scale (AIMS) Movement Rating Score, and Barnes Akathisia Rating Scale (BARS) Global Score, and Sheehan Suicidality Tracking Scale (Sheehan-STS).

Protocol 331-201-00182

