3.11 Subject Compliance

Responsible trial personnel will dispense the IMP (ie, brexpiprazole) according to the visits outlined in the Schedule of Assessments ([Table 3.6-1](#)). Accountability and compliance verification should be documented in the subject’s trial records.

The importance of taking the IMP as directed should be emphasized at all trial visits. If poor compliance continues (eg, dosing errors resulting in overall compliance less than 80% or greater than 120%), discontinuation of the subject from the trial should be considered in consultation with the medical monitor.

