3.12 Protocol Deviations

In the event of a significant deviation from the protocol due to an emergency, accident, or mistake (eg, violation of informed consent process, IMP dispensing or subject dosing error, treatment assignment error, subject enrolled in violation of eligibility criteria or concomitant medication criteria), the investigator or designee will contact the sponsor’s designee (medical monitor) at the earliest possible time. The investigator and sponsor’s designee will come as quickly as possible to a joint decision regarding the subject’s continuation in the trial. This decision will be documented by the investigator and the sponsor’s designee, and reviewed by the site monitor.

4 Restrictions

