6.3 Protocol Deviation

Protocol deviations including the types of deviations (eg, deviations in entry criteria, dosing, concomitant medications, procedurals, etc.) will be summarized on the Enrolled Sample by trial center, and prior treatment group. A listing of protocol deviations will be provided.

7 Baseline Characteristics

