9.9 Extent of Exposure

The start date of open-label IMP will be the first day of open-label IMP dosing. The number and percentage of subjects who receive open-label IMP will be presented by week and by parent study treatment group. Each dosing week will be based on the actual week; i.e., Day 1 to 7 in Week 1, Day 8 to 14 in Week 2, etc. This summary will be performed on the Safety Sample.

The number and percentage of completers will be presented by week and by parent study treatment group.

The mean daily dosage will be summarized by week and parent study treatment group using descriptive statistics. The mean daily dosage per subject per week will be determined for each week of the trial. This will be calculated by dividing the sum of individual total doses by the number of days in the week interval. The summary will contain for each parent study treatment group the number of subjects receiving open-label IMP, and the mean and range of the mean daily dose for each week.

10 Conventions

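### Does the SAP compliance table need an upper cut-off at 120% to match the protocol's example of poor compliance?

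*SAP*

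**What the plan says.** SAP 6.2 (Treatment Compliance) calculates compliance by "dividing the number of tablets taken by the total number of tablets the subjects were scheduled to take during the trial period". It then tabulates the "Number (%) of subjects meeting compliance cut-offs" as below 70%, 70% to below 80%, 80% to below 90%, and 90% or more. Nothing caps the ratio at 100%, and the SAP does not mention 120% anywhere.

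Protocol 3.11 (Subject Compliance) tells sites that if poor compliance continues, discontinuation should be considered together with the medical monitor. Its example of poor compliance is "eg, dosing errors resulting in overall compliance less than 80% or greater than 120" per cent.

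Three other places bear on excess intake:

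- Protocol 3.12 includes "IMP dispensing or subject dosing error" among the significant deviations to be taken to the medical monitor. SAP 6.3 summarises and lists deviations by type ("deviations in entry criteria, dosing, concomitant medications, procedurals, etc").
- SAP 9.9 reports, for each parent-study treatment group, "the mean and range of the mean daily dose for each week".
- SAP 3.2 limits upward changes: "one dose increase is permitted but only at the Week 6 scheduled visit".

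On supply, the protocol synopsis states: "Each dose will be supplied in blister cards containing sufficient tablets for 7 (+2) days". Protocol 8.4 has dispensed cards returned at each visit.

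**The concern.** The protocol's example range has two sides and the SAP table shows only one. Adding the two lowest rows gives everyone below 80%. The upper side cannot be recovered, because 95%, 105% and 125% all fall in the best row.

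The trial's only objective is safety and tolerability. Intake above schedule is useful context for reading adverse events, and the one planned compliance table gives three rows to under-use and none to over-use. Subjects whom the protocol would use to illustrate poor compliance would be presented as good compliers. Splitting the last row would cost almost nothing, since the tablet counts are already needed for the ratio.

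**Working it through.** **1. The two classifications side by side**

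| Compliance | SAP 6.2 row | Protocol 3.11 example |
|---|---|---|
| 75% | 70% to below 80% | poor |
| 85% | 80% to below 90% | not poor |
| 100% | 90% or more | not poor |
| 120% | 90% or more | not poor |
| 120.1% | 90% or more | poor |
| 125% | 90% or more | poor |

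They differ only above 120%.

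**2. Is more than 120% reachable?** Yes. A card holds doses for 7 + 2 = 9 days, and 9 doses in 7 scheduled days is 9/7 = 128.6%. This is not a maximum: a subject who stops on day 5 having taken all 9 has 9/5 = 180%.

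The number of cards per visit is not stated. Assume one card per scheduled week, which gives 2 spare doses a week. The fewest doses above 120% is the smallest whole number greater than 1.2 × scheduled days:

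| Scheduled days | 1.2 × days | Doses needed | Extra doses | Spare doses |
|---|---|---|---|---|
| 7 | 8.4 | 9 | 2 | 2 |
| 14 | 16.8 | 17 | 3 | 4 |
| 42 | 50.4 | 51 | 9 | 12 |
| 84 | 100.8 | 101 | 17 | 24 |

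An early dropout can pass 120% on two extra doses. A completer must use 17 of 24 spares.

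**3. Would the weekly dose range show it?** Assume weekly doses are built from doses actually taken, and that 3 mg/day is the highest permitted dose (2 and 3 mg/day are the only target doses named). The range reveals excess when a subject's weekly mean exceeds the highest dose permitted to anyone in that group that week.

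- On 3 mg/day at 120%: 3 × 1.2 = 3.6 mg, above any permitted dose in any week.
- Parent 2 mg group before the Week 6 visit: no increase is allowed, so any weekly maximum above 2 mg has no permitted explanation. At 120% the mean is 2 × 1.2 = 2.4 mg.
- Parent 2 mg group after Week 6: 2.4 mg lies below the 3 mg reached by permitted increases, so the range can mask it. With visits on their target days, Weeks 7 to 12 supply at most 6 × 2 = 12 spare doses. A completer above 120% therefore takes at least 17 − 12 = 5 extras in Weeks 1 to 6. At least one of those weeks has 8 or more doses, a mean of at least 8/7 × 2 = 2.29 mg, which is visible against 2 mg. The ±2-day visit windows shift these counts slightly and could hide a marginal case.
- Masking is also possible for a subject reduced from 3 to 2 mg/day, which is allowed from Week 4. It is possible too among former placebo subjects if that group contains both doses.

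**4. Does anything downstream use compliance?** The three samples in SAP 5.1 rest on consent and enrolment, on at least one dose, and on having baseline and post-baseline CMAI scores. The adverse event tables in SAP 9.1 use the Safety Sample. None refers to compliance.

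**The case for a change.** The strongest case for a change is that 80% to 120% is the only numeric compliance range in the protocol, and the SAP keeps one end and drops the other without giving a reason. The alternative routes are imperfect. SAP 6.3 sets no compliance threshold, and cumulative over-use need not be logged as a deviation. SAP 9.9 gives only the weekly extremes, which can be masked for some subjects on 2 mg/day. Neither yields a count, so even a count of zero could not be stated from the planned tables.

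All of that stands as a description of the table. It does not show that the plan would mislead. The 90%-or-more row is accurate as labelled. The 120% figure is introduced as an example within an instruction to sites, and a descriptive table need not reproduce every illustrative threshold of a conduct rule. Nor is over-use hidden altogether: dosing errors have a deviation route, and the weekly range exposes excess in the 3 mg/day group throughout and in the parent 2 mg group before Week 6.

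**Conclusion.** The table does not count subjects above 120%, and that is the full extent of the point. No analysis set, adverse event estimate or conclusion depends on it. The plan as written gives sound results, so no amendment is warranted.

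The number of subjects concerned cannot be obtained from the documents and may be zero. Under the one-card-per-week assumption, a completer would need at least 17 extra doses, while a subject stopping at Week 1 would need 2. What could pass unseen in the dose range is confined to subjects on 2 mg/day in a group and week where others may properly be on 3 mg/day. That statement assumes weekly doses reflect actual intake and 3 mg/day is the top dose.

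If anyone wants the count when the study report is written, it comes directly from the ratios already calculated under SAP 6.2. Showing it would be a presentational choice.

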6.3 Protocol Deviation

Protocol deviations including the types of deviations (eg, deviations in entry criteria, dosing, concomitant medications, procedurals, etc.) will be summarized on the Enrolled Sample by trial center, and prior treatment group. A listing of protocol deviations will be provided.

7 Baseline Characteristics

7.1 Baseline Definition

Individual subject's baseline value is defined as the observation or assessment taken on the subject at the last scheduled visit (i.e., the Week 12 visit) in the double-blind treatment period of the parent trial (Trial 331-14-213). There will be no imputation for baseline values if missing or unknown.

7.2 Demographic Characteristics

Demographic and baseline characteristics including age, race, ethnicity, gender, weight, height, waist circumference, and body mass index (BMI) will be summarized by descriptive statistics (frequency, mean, median, standard deviation, maximum, minimum, and percentage when applicable) for the Enrolled Sample by parent study treatment group and overall.

7.3 Baseline Psychiatric Evaluations

Baseline psychiatric evaluations for the open-label extension trial are the ones taken at the last assessment visit of the parent trial. The baseline values in the following parameters will be summarized on the OC data on the Enrolled Sample using descriptive statistics: CMAI total score; CMAI derived agitation factors of aggressive behavior, physically nonaggressive behavior, and verbally agitated behavior; Clinical Global Impression-Severity of Illness Scale (CGI-S) score, MMSE score, Sheehan Suicidality Tracking Scale (Sheehan-STS) score. Refer to [Section 10](#) for all the scales and the scoring via the aggregation of component items of the scales.

SAP 331-201-00182

8.1 COVID-19 Related Supplementary Analyses

Summary statistics for mean and mean change from baseline in CMAI total score, by trial visit and at the last visit (i.e., Week 12/ET) and by visit type (face-to-face vs. remote) based on the Efficacy Sample will be provided by parent study treatment group for rollover subjects and overall.

9 Safety Analysis

The primary safety endpoint analysis is the frequency and severity of AEs in the open-label treatment phase (see [Section 9.1](#)). Other standard safety variables to be analyzed include clinical laboratory tests, vital signs, body weight, waist circumference, BMI, 12-lead electrocardiograms (ECGs), and physical examinations. In addition, data from the following safety scales will be evaluated: MMSE score, assessments of suicidality (eg, Sheehan-STS), and extrapyramidal symptoms (EPS; eg, the Simpson-Angus Scale, abnormal involuntary movement scale [AIMS], and Barnes Akathisia Rating Scale [BARS]).

Safety analyses will be conducted based on the Safety Sample, and summary statistics will be provided by parent study treatment group and overall, unless otherwise specified.

The long-term 24 weeks (6 months) safety analysis for subjects who received brexpiprazole in the parent trial 331-14-213 will be described in the SAP for the Summary of Clinical Safety (SCS) for Agitation in Alzheimer's dementia (AAD) and the results will be presented in the SCS.

Unless otherwise specified, in general, analysis of safety data will be performed on observed case and for last visit.

SAP 331-201-00182

9.1 Adverse Events

All adverse events will be coded by System Organ Class (SOC) and Preferred Term (PT) according to the Medical Dictionary for Regulatory Activities (MedDRA). AEs that are sex-specific, eg, ovarian cancer, will have their incidence rates evaluated for the specific sex.

Treatment-emergent AEs (TEAEs) are defined as AEs with an onset date on or after the first dose of IMP. In more detail, TEAEs are all adverse events which started after start of IMP; or if the event was continuous from baseline and was worsening, serious, study drug related, or resulted in death, discontinuation, interruption or reduction of study therapy. Adverse events occurring up to 30 days after the last day of IMP will be included in the summary tables.

The incidence of the following events in the open-label treatment phase will be tabulated by treatment group and overall using the Safety Sample:

- a) Treatment-emergent AEs (TEAEs)
- b) TEAEs by severity
- c) TEAEs potentially causally related to the IMP
- d) TEAEs with an outcome of death
- e) Serious TEAEs
- f) TEAEs leading to discontinuation of the IMP

The above summaries (b), (e) and (f) will also be prepared for TEAEs potentially causally related to the IMP.

In addition, incidence of TEAE during the open-label treatment phase of at least 5% by SOC and PT will be provided.

Incidence of TEAEs by SOC and PT will be summarized for sex, race, age and region subgroups.

Extrapyramidal symptoms (EPS)-related AEs will be grouped into five categories.

1) Dystonic Events, which include blepharospasm, cervical spasm, clumsiness, dystonia, dystonic tremor, emprosthotonus, essential tremor, facial spasm, fumbling, gait inability, head titubation, intention tremor, Meige's syndrome, muscle contractions involuntary, muscle spasms, muscle spasticity, muscle tightness, muscle tone disorder, musculoskeletal stiffness, myotonia, nuchal rigidity, oculogyration, oesophageal spasm, opisthotonus, opisthotonus, oromandibular dystonia, oropharyngeal spasm, pharyngeal dystonia, pleurothotonus, risus

SAP 331-201-00182

sardonicus, spasmodic dysphonia, tongue spasm, torticollis, torticollis psychogenic, trismus, uvular spasm;

2) Parkinsonian Events, which include action tremor, akinesia, asterixis, bradykinesia, bradyphrenia, cogwheel rigidity, dysphonia, fine motor skill dysfunction, freezing phenomenon, gait disturbance, gait festinating, hypertonia, hypokinetic dysarthria, laryngeal tremor, masked facies, micrographia, mobility decreased, muscle rigidity, on and off phenomenon, parkinsonian crisis, parkinsonian gait, parkinsonian rest tremor, parkinsonism, parkinsonism hyperpyrexia syndrome, parkinsons disease, parkinson's disease, parkinson's disease psychosis, postural reflex impairment, postural tremor, propulsive gait, reduced facial expression, resting tremor, tremor, walking disability;

3) Akathisia Events, which include akathisia, extrapyramidal disorder, hyperkinesia, movement disorder, psychomotor hyperactivity, and restlessness;

4) Dyskinetic Events, which include abnormal involuntary movement scale, athetosis, ballismus, buccoglossal syndrome, chorea, choreoathetosis, chronic tic disorder, complex tic, dopamine dysregulation syndrome, drooling, dyskinesia, dyskinesia oesophageal, grimacing, motor dysfunction, muscle twitching, nodding of head, oculogyric crisis, pharyngeal dyskinesia, protrusion tongue, provisional tic disorder, rabbit syndrome, respiratory dyskinesia, secondary tic, tardive dyskinesia, tic;

5) Residual Events, which include huntingtons disease and myoclonus.

Unless otherwise specified, in general, analysis of safety data will be performed on observed case and for last visit.

Unless otherwise specified, in general, analysis of safety data will be performed on observed case and for last visit.

